11.5.3 Cost Effectiveness Analysis

For the primary analysis, we will estimate cost accumulated within 2 years. A larger limit is possible if we have a reasonable number of people surviving at that time.

Since patients are enrolled into the study over time and some patients are still alive at the end of the study, so their survival time and costs are censored. Due to the presence censoring, we cannot use a simple average of the patients' total costs, a simple average of the patients' costs for those with complete cost information, or a Kaplan-Meier estimator on censored costs, since these all produce biased estimators of the mean costs[34]. Instead, we will use the inverse-probability weighting method to calculate average costs for each treatment group.[35, 36] The assumption used in this method is that censoring is independent of the survival time, or cost collection process, which is often satisfied in wellconducted clinical trials. If the new treatment can both extend patients' survival time (or quality-adjusted survival time), and save costs at the same time, the new treatment will be preferred to the current standard treatment under any willingness to pay threshold. However, if the new treatment extends survival time but costs more, cost-effectiveness analysis provides an estimate of the incremental cost of greater incremental effectiveness. For traditional cost-effectiveness analysis, treatment effectiveness is measured simply as survival time. The incremental cost-effectiveness ratio indicates the additional cost required to attain one additional year of survival. For cost-utility analysis, treatment effectiveness is measured as quality-adjusted survival time (which accounts for the impact of treatment on both mortality and morbidity, including any differences in adverse affects of treatment affecting HR-QoL). For cost-utility analysis, the incremental costeffectiveness ratio indicates the additional cost required to attain one additional year of quality adjusted survival.

11.5.4 Quality-Adjusted Survival Time

The quality-adjusted survival time estimates need to account for the presence of censoring. Due to the induced informative censoring problem, the ordinary survival method (e.g.,

Kaplan-Meier estimator) cannot be applied in this case.[35-37] Accordingly, we will use the inverse-probability weighted method of Zhao and Tsiatis to carry out the survival time analysis.[35, 36] To estimate quality adjusted survival time, data from EQ-5D will first be translated into utility measures. These measures are obtained at discrete time points, so they will be interpolated into the time intervals between the visits. The quality-adjusted survival time is just an integration of the utility measures over a patient's survival time, or until the time limit similar as the cost calculation, whichever occurs earlier.

11.5.5 Projection Model and Sensitivity Analysis

If the new treatment is implemented in usual practice, some of its potential benefits to patients may extend beyond the time horizon of the clinical trial. We will explore the potential to use results from the clinical trial based cost-effectiveness analysis, augmented with information from secondary sources, to develop a model to project costs and effectiveness beyond the time horizon included in the clinical trial. Any such model projections would be subjected to probabilistic sensitivity analysis, to assess the impact of parameter uncertainty on estimated cost effectiveness results.

11.5.6 Progression-Free Survival (PFS) and Time to Local Progression

The time to disease progression and time to local regression will be estimated using the Kaplan-Meier approach. The stratified log-rank test will be used to test for a statistically significant difference in PFS and time to local progression distributions. The null and alternative hypotheses are H_0 : $S_1(t) < S_2(t)$ vs. H_A : $S_1(t) \ge S_2(t)$, where $S_i(t)$ is the distribution of survival times for patients in arm i. The Cox proportional hazard regression model will be used to determine hazard ratios and 95% confidence intervals for the treatment difference in progression-free survival and time to local progression. Unadjusted ratios and ratios adjusted for stratification variables and other covariates of interest will be computed.

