2.2 Secondary Objectives

2.2.1 To compare toxicity, time to local progression, disease-free survival, quality of life, cost effectiveness, and quality adjusted life of two radiotherapy treatment regimens in patients with stage II-III or recurrent NSCLC and poor performance status.

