9.6 Other response parameters

- **9.6.1** Time to Local Progression: The time to progression will be measured from the date of study enrollment to the date of documented local progression as determined by clinical exam and imaging studies.
- **9.6.2** Overall Survival: The survival time will be measured from the date of study enrollment to the date of death. All patients will be followed for survival. Every effort should be made to document the cause of death.
- **9.6.3** Progression Free Survival: Progression free survival will be measured from the date of study enrollment to the date occurrence of local or regional progression, distant metastases, or death from any cause.

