11.1.2.4 Toxicity: Grade 3-5 adverse events as graded by CTCAE v 4.0

11.2 Sample Size Determination

The sample size calculation is based on the primary endpoint, overall survival at 1 year, and the assumption that patients are randomized until the end of accrual. The sample size is calculated with the 2-sided significance level of 0.05 and 80% statistical power using a 2-sample log rank test. We assume that the overall survival function follows an exponential distribution for each arm. Accrual to the study is assumed to be uniformly distributed. The null hypothesis is that the there are no difference in 1-year survival rates between two arms. We assume that the patients will be accrued for 2 years with a 1-year follow-up. We hypothesize that the patients randomly assigned to the control arm and experimental arm have a 1-year survival rate of 45% (hazard rate [λc]) of 0.799) and 60% (hazard rate [λe]) of 0.511), respectively, which is translated to the hazard ratio of $\lambda e/\lambda c = 0.640$. One interim analysis and a final analysis are planned for early stopping for efficacy. The efficacy testing is based on the Lan-DeMets spending function, which resembles the O'Brien-Fleming boundary. The total sample size of 226 patients (113 in the control arm and 113 in the experimental arm) will be accrued to achieve the desired 80% statistical power and 2-sided significance level of 0.05. Guarding against ineligibility or lack-ofdata rate of up to 5%, the final targeted accrual for this study will be 238 patients (119 per arm). Sample size was estimated using the sample size software EaST version 5.

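### Time to local progression is planned by Kaplan-Meier with no rule for deaths without local progression; if these are censored, the complement of the curve overstates the actual probability of local failure

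*Combined protocol and SAP*

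**What the plan says.** Time to local progression belongs to the secondary objective in 2.2.1: "To compare toxicity, time to local progression, disease-free survival, quality of life, cost effectiveness, and quality adjusted life of two radiotherapy treatment regimens". Section 9.6.1 defines it: "The time to progression will be measured from the date of study enrollment to the date of documented local progression". Death is not part of that event. In the same section, 9.6.3 does count death for progression-free survival, whose event is "occurrence of local or regional progression, distant metastases, or death from any cause".

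Section 11.5.6 gives the analysis: "The time to disease progression and time to local regression will be estimated using the Kaplan-Meier approach". I read the word regression as a slip, because the section title and the next sentence refer to local progression: "The stratified log-rank test will be used to test for a statistically significant difference in PFS and time to local progression distributions". A Cox model is also planned.

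No section gives a censoring rule for patients who die without local progression, and none names cumulative incidence or another competing-risk method. The plan does set Kaplan-Meier aside elsewhere, for censored costs (11.5.3) and for quality-adjusted survival (11.5.4). The reasons there are different, and 11.5.6 has no similar provision.

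**The concern.** A Kaplan-Meier analysis must treat each death as an event or as a censoring. Section 9.6.1 excludes it as an event, which leaves censoring. A patient who has died can no longer fail locally, but a censored patient is treated as still able to. One minus Kaplan-Meier then does not estimate the proportion of patients who fail locally. At best it describes a setting in which nobody dies first.

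This matters because early death is common in this population and the assumed mortality differs between arms. Section 1.1 presents local failure as the unsolved problem of radiotherapy, so readers will look at the local failure curves. If they read them as actual risk, the figures will be too high, and by different factors in the two arms.

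**Working it through.** **Inputs from the documents.** Section 11.2 assumes that control and experimental patients "have a 1-year survival rate of 45% (hazard rate [λc]) of 0.799) and 60% (hazard rate [λe]) of 0.511". Accrual is 2 years with 1 further year of follow-up, at two-sided 0.05 and 80% power, with 226 patients.

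**Reproducing the plan's figure.**
- Hazards: −ln(0.45) = 0.799 and −ln(0.60) = 0.511, so the hazard ratio is 0.640.
- Events (Schoenfeld): 4 × (1.960 + 0.842)² / (ln 0.640)² ≈ 157.3, so 158.
- Probability of death during the study: 1 − (e^(−λ) − e^(−3λ))/(2λ) = 0.775 and 0.624, mean 0.700.
- N = 158/0.6997 = 225.8, so 226. Allowing 5%: 226/0.95 = 237.9, so 238.

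The death hazards are therefore the ones behind the stated sample size.

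**Assumptions, not in the documents.**
- Constant hazards.
- A local progression hazard L of 0.2, 0.4 or 0.6 per year, equal in both arms. The plan makes no assumption about local failure. Section 1.1 cites 22-50% from other studies, without a time point or estimator.
- A hazard D of death without local progression. I use the overall death hazard. It includes deaths after local progression, so it is an upper bound as long as local progression does not lower mortality.

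**Formulas.**
- One minus Kaplan-Meier, deaths censored: 1 − exp(−L·t).
- Cumulative incidence, death competing: L/(L + D) × [1 − exp(−(L + D)·t)].

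**Worked case, L = 0.4, t = 2 years.**
- One minus Kaplan-Meier, both arms: 1 − exp(−0.8) = 55.1%.
- Control: 0.4/1.199 × (1 − exp(−2.398)) = 0.3336 × 0.9091 = 30.3%. Ratio 1.82.
- Experimental: 0.4/0.911 × (1 − exp(−1.822)) = 0.4391 × 0.8383 = 36.8%. Ratio 1.50.

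| L per year | Time | D | 1 − KM | Cumulative incidence, control / experimental | Ratio, control / experimental |
|---|---|---|---|---|---|
| 0.2 | 2 y | full | 33.0% | 17.3% / 21.3% | 1.90 / 1.54 |
| 0.4 | 2 y | full | 55.1% | 30.3% / 36.8% | 1.82 / 1.50 |
| 0.6 | 2 y | full | 69.9% | 40.3% / 48.2% | 1.74 / 1.45 |
| 0.4 | 1 y | full | 33.0% | 23.3% / 26.2% | 1.41 / 1.26 |
| 0.4 | 2 y | half (0.3995 / 0.2555) | 55.1% | 39.9% / 44.6% | 1.38 / 1.24 |

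**Second way of setting L.** Suppose instead that the cited 22-50% were Kaplan-Meier figures at 2 years. With the full death hazards the 2-year ratios are 1.84 to 1.94 (control) and 1.51 to 1.56 (experimental). At 36%, L = −ln(0.64)/2 = 0.223 and cumulative incidence is 19.0% and 23.4%.

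**The case against.** Four points can be made on the other side.

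1. *The plan does not say that deaths are censored.* This is correct. Censoring is inferred from the event definition together with the estimator. The firm finding is that the handling of death is unspecified. Counting death as an event would give a different endpoint and contradict 9.6.1.

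2. *The size depends on assumptions.* This stands. A reader might take the control-arm result at 2 years and conclude that local failure is overstated nearly two-fold in general. The documents do not support that. The experimental-arm ratio is about 1.5, the 1-year ratios are lower, and the full death hazard is an upper bound. The local hazards are assumed, and only the 22-50% in 1.1 is available for comparison.

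3. *The treatment comparison is sound.* This also stands. A reader might infer that the log-rank and Cox results are invalid. They are not, because with deaths censored they compare cause-specific hazards. That is the relevant comparison for whether the experimental regimen controls the tumour better. In the worked case local hazards are equal and Kaplan-Meier correctly shows one curve. Cumulative incidence is higher in the experimental arm (36.8% against 30.3%) only because its patients live longer. Cumulative incidence is needed for absolute risk, not for the mechanism.

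4. *The consequence is limited.* The objective is a comparison, no local failure rate at a fixed time is planned, and time to local progression is missing from the endpoint list in 11.1.2. This limits the weight of the point. However, a Kaplan-Meier estimate is planned, and its complement is readily read as the proportion failing.

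**Conclusion.** The concern holds for the absolute local failure curves. The event in 9.6.1 excludes death, 11.5.6 prescribes Kaplan-Meier, and no competing-risk method is given. If deaths are censored and the curve is read as actual risk, the direction of the error is certain: local failure is overstated.

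The size is conditional. With constant hazards, the plan's overall death hazards as an upper bound and L of 0.2 to 0.6 per year, the factor at 2 years is about 1.7 to 1.9 in the control arm and about 1.5 in the experimental arm. Setting L from the cited 22-50% moves the upper ends only to 1.94 and 1.56. At L = 0.4 the factors are about 1.4 and 1.3 at 1 year. With half the death hazard they are about 1.4 and 1.2 at 2 years.

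The point does not reach the stratified log-rank and Cox comparison, the primary endpoint, or progression-free survival as defined in 9.6.3. It should be corrected because the remedy is nearly free, but it does not threaten the trial's main conclusion.

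**What to change.** In 11.5.6:
- State that death without local progression is a competing event for time to local progression.
- Report local progression by arm with the cumulative incidence function (Aalen-Johansen estimator) in place of one minus Kaplan-Meier.
- Keep the stratified log-rank test and Cox model as the treatment comparison, and label them cause-specific.
- Use Gray's test or a Fine-Gray model at most as supportive, noting that each also reflects differences in mortality between arms.
- Correct the word regression to progression.

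The cost is a few lines of text and standard software. It uses dates of death and local progression that the trial already collects, and the sample size does not change. The visible downside is that the reported local failure figures will be lower than Kaplan-Meier figures would have been.

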11.5.7 Toxicity

Any subject who receives treatment on this protocol will be evaluable for toxicity. Each patient will be assessed for the development of toxicity according to the Time and Events table (Appendix II). Toxicity will be assessed according to the NCI Common Toxicity Criteria for Adverse Events (CTCAE), version 4.0. Dose adjustments should be made according to the system showing the greatest degree of toxicity.

Only adverse events assessed to be definitely, probably, or possibly related to protocol treatment will be considered. The rates of all Grade 3-5 adverse events, and death during or within 30 days of discontinuation of protocol treatment will be tested for equality using a two-sided chi-square test with a 0.05 significance level.

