Standard radiation to the chest for unresectable stage III NSCLC is 60-66 Gy at 2 Gy per fraction. Radiobiologic calculations indicate that the accelerated therapy regimen of 3 Gy/fraction to 45 Gy is similar to 2 Gy per fraction to 60 Gy, with regrowth delay time (time to progression) of 92% and late complication biologically effective dose (BED) of 90% of that calculated for standard radiation. Additionally, 45 Gy at 3 Gy per fraction has been shown to have similar clinical outcomes and toxicity. This has been shown in a retrospective review at MD Anderson of 2 cohorts of node positive patients with inoperable LA-NSCLC treated with radiation alone [22]. One cohort (26 patients) had borderline prognostic factors (KPS < 70 but > 50 and/or weight loss of more than 5%) and was treated to 45 Gy over 3 weeks at 3 Gy/fraction. The second cohort (29 patients) had significantly better prognostic factors and was treated to 60-66 Gy over 6 to 6.5 weeks at 2 Gy per fraction during the same period. Despite having worse prognostic factors, the cohort treated to 45 Gy at 3 Gy per fraction over 3 weeks had response rates, locoregional control, and overall survival comparable to those in the cohort treated to a total dose of 60-66 Gy at 2 Gy per fraction over 6 weeks without difference in acute or late toxicity. Radiation dose intensification in locally advanced NSCLC has been studied in prospective trials. Slotman et.al. treated 301 stage III NSCLC patients with three different hypofractionated radiation therapy regimens of 40 Gy in 8-10 fractions with a one week break, 30-32 Gy in 6 fractions or 24 Gy in 3 fractions. These regimens were all well tolerated.[23] A group from Poland found similar toxicity profiles in patients treated with 21 fractions of radiation using 2.7, 2.8 and 2.9 Gy fractions. Of those patients, 7% had grade III acute esophageal toxicity and 6% had grade III or greater late pulmonary toxicity [24]. An Italian group reported a 30 patient trial wherein 60 Gy in 20 fractions was given to patients with locally advanced NSCLC. Grade 3 hematological toxicity occurred in 1 patient, grade 3 esophagitis in 1 patient and grade 3 pneumonitis in 2 patients [25]. Subsequently, the MD Anderson group reported a phase I trial evaluating 45, 52.5 and 60 Gy delivered in 15 fractions using proton beam and found similar, acceptable levels of toxicity in all arms[26]. Collectively, this information support both our trial concept and the dose intensity utilized.

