6.1.2 Dose Fractionation for Arm A

Patients on Arm A will receive 15 fractions of radiation. Patients will receive 4.0 Gy per fraction for 15 fractions (total dose = 60 Gy). All fields must be treated daily. Plan adaptation for treatment response is allowed and encouraged. (see Section 6.1.1)

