6.2.2 Dose Fractionation for Arm B

Patients on Arm B will receive 30-33 fractions of radiation at 2 Gy per fraction (total dose 60-66 Gy). There will be no field reductions, and all fields must be treated daily including the entire PTV treated daily.

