6.9 Radiation Adverse Events

Adverse Events will be categorized and graded based primarily on the Common Toxicity Criteria for adverse events Version 4.0 (CTCAE version 4.0) with the exception of changes in pulmonary function tests (see section 6.9.4 below).

Radiotherapy should be interrupted for Grade 4 in-field toxicity and resumed when that toxicity has decreased to Grade ≤ 2 as detailed below. If treatment is interrupted for > two weeks, the patient should be removed from study treatment.

6.9.1 Reversible or permanent alopecia, bone marrow toxicity, skin pigmentation, and esophagitis are expected side effects of radiation therapy. Radiation induced myocarditis or transverse myelitis rarely occur at doses lower than 50 Gy. Radiographic evidence of radiation change and subsequent fibrosis of the lung will occur within lung volume receiving ≥20 Gy, usually within the first six months after initiation of treatment. It is essential to spare as much normal lung as possible in order to avoid symptomatic lung injury.

Adverse Event Monitoring

Adverse event data collection and reporting, which are required as part of every clinical trial, are done to ensure the safety of subjects enrolled in the studies as well as those who will enroll in future studies. Adverse events are reported in a routine manner at scheduled times during a trial. Additionally, certain adverse events must be reported in an expedited manner to allow for optimal monitoring of subject safety and care.

All subjects experiencing an adverse event, regardless of its relationship to study therapy, will be monitored until:

- the adverse event resolves or the symptoms or signs that constitute the adverse event return to baseline or is stable in the opinion of the investigator;
- > there is a satisfactory explanation other than the study therapy for the changes observed; or
- death.

Definitions

An adverse event is defined as any untoward or unfavorable medical occurrence in a human research study participant, including any abnormal sign (for example, abnormal physical exam, imaging finding or clinically significant laboratory finding), symptom, clinical event, or disease, temporarily associated with the subject's participation in the research, whether or not it is considered related to the subject's participation in the research.

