6.9.2 Esophagitis

Esophageal complaints are common with thoracic radiation therapy. Esophagitis does not constitute a reason to interrupt or delay radiotherapy provided oral intake is sufficient to maintain hydration. Patients should be advised to avoid alcoholic, acidic, or spicy foods or beverages. Viscous Xylocaine, Carafate, or other medications should be used for symptomatic relief. Occasionally, narcotics may be required.

It is not necessary to biopsy acute esophagitis in the first 2 weeks of therapy since it is rarely due to underlying viral or fungal disease. Acute esophagitis may persist for 4-6 weeks. If Grade 3 or 4 esophagitis occurs, and a treatment interruption is being considered, every effort should be made to limit it to 3 treatment days or less. Patients requiring hospitalization because of esophagitis may have their treatment interrupted. In this event, please notify [name].

Esophagitis should be graded according to the CTCAE v.4.0

Table 4. Esophagitis grading system

 	nagino grading oyotom
Grade	Clinical Scenario
1	Asymptomatic pathologic, radiographic, or endoscopic findings only
2	Symptomatic; altered eating/swallowing (e.g., altered dietary habits, oral
	supplements), IV fluids indicated <24 hrs
3	Symptomatic and severely altered eating/swallowing (e.g., inadequate oral
	caloric or fluid intake), IV fluids, tube feedings, or TPN indicated >24 hrs
4	Life-threatening consequences; urgent operative intervention indicated
5	Death

Treatment should be interrupted for grade 4 or greater dysphagia or odynophagia. Acute esophageal toxicity, which typically can occur within two weeks of the initiation of treatment and manifests as dysphagia, odynophagia, reflux symptoms, etc. should be pharmacologically managed with the following approach and should be initiated at the first signs or symptoms of esophageal toxicity. Recommended treatments are as follows:

- 1) Ketoconazole 200 mg PO q day OR Fluconazole 100 mg PO q day until the completion of radiation.
- 2) Mixture of: 2% viscous lidocaine: 60 cc, Mylanta: 30 cc, sucralfate (1 gm/cc): 10 cc; Take 15-30 cc PO q3-4 hrs prn. (Contraindications: pts on Dilantin, Cipro, Digoxin)
- 3) Ranitidine 150 mg PO BID (or other H2 blocker or a proton pump inhibitor such as omeprazole) until the completion of radiation
- 4) Grade 4 esophagitis: hold XRT until grade 2 or less. We expect a significant portion of patients will experience grade 3 esophagitis.

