10.0 Data Collection

Patient, treatment, HRQOL, and patient perspective costs data (Appendix VII) should be submitted to:

Department of Radiation Oncology
Clinical Research Office
The University of Texas Southwestern Medical Center
Attention: [name], Project Manager
[name]
[name]
[contact]

Economic data (patient bills, and other cost documents) will be collected by:

Department of Epidemiology and Biostatistics School of Rural Public Health Texas A&M Health Science Center, [name]

Attn: [name] [name] [name]

Patients will be identified only by initials (first middle last) and a unique study ID number assigned to each study participant; if there is no middle initial, a hyphen will be used (first-last). Last names with apostrophes will be identified by the first letter of the last name. Identifiable information will be released to Drs. [name] and [name] at Department of Epidemiology and Biostatistics, Texas A&M Health Science Center (TAMHSC) for obtaining the bills that are associated with each service reported in the case report forms.

Item	Due
Demographics	Within 2 weeks of study enrollment
Eligibility and Entry Characteristics, including baseline H&P and Zubrod PS	Within 2 weeks of study enrollment
Pathology Report	Within 2 weeks of study enrollment
Follow-up H&P data	At post XRT follow-up at 1, 3, 6, 9, and 12 months, then q 4 months year 2, then q6 months years 3-5; then annually
Tumor response evaluation	At post XRT follow-up at 3, 6, 9, and 12 months, then q 4 months year 2, then q6 months years 3-5; then annually
Adverse Event assessment	After each weekly treatment visit, then post XRT follow-up at 1, 3, 6, 9, and 12 months, then q 4 months year 2, then q6 months years 3-5; then annually
Healthcare Utilization/Cost Worksheet (Appendix VI),	Within 2 weeks of study enrollment, at the end of treatment, and at post treatment follow up at 1, 3, 6, 9, and 12 months, then q 4 months year 2, then q6 months years 3-5; then annually until death
FACT-L (Appendix VIII), EQ-5D (Appendix IX)	Within 2 weeks of study enrollment, at the end of treatment, and at post treatment follow up at 6 and 12 months,
Patient Perspective Cost Assessment (Appendix VII)	Upon radiation completion or first possible post treatment follow up (1 month). To be administered just once.

Data collection for QA

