Appendix II: Study Parameter Table

				During XRT		Fo	ollow-Up	(months a	fter therap	yy)
		Within 12 weeks prior to registration/ study enrollment	prior to XRT	Weekly	1 month	3 months	6 months	9 months	12 months	Q 4 months during year 2, then q 6 months years 3-5, then annually
History / Physical		X		Х	Х	Х	Х	Х	Х	Х
Zubrod PS		Х		Х	Х	Х	Х	Х	Х	Х
Weight		Х		Χ	Х	Х	Х	Х	Х	X
Biopsy/ cytology	X ³									
CT of Chest ¹		Х				X	Х	X	Х	X
MRI Brain ²		X								
PFT's (including DLCO and FEV1)		X					X		Х	
CBC w/ diff		Х								
Serum or urine pregnancy test (if applicable)		X ⁵								
Informed consent	Х									
Comorbidity index (Appendix V)		Х								
Adverse event evaluation				Х	Х	X	Х	Х	Х	X
Tumor response evaluation						Х	Х	Х	Х	X
FACT-L and EQ-5D			Х	X ⁶			Х		Х	
Healthcare Utilization/ Cost Worksheet			Х	X ⁶	Х	Х	Х	Х	X	Х
Patient Perspective Cost Assessment				X ⁴ (last week only)	X ⁴					

 $^{^{1}\!}Preferably$ with IV contrast unless medically contraindicated $^{2}\!CT$ if MRI medically contraindicated

³ Within 9 months of study enrollment

⁴Upon completion or first follow up

⁵ within 14 days of registration/study enrollment

⁶At end of treatment

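### Adverse event visits, the acute period and the 30-day death window are all timed from the end of radiation, which differs by arm, so Section 11.5.7 compares toxicity and early death over unequal windows

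*Combined protocol and SAP*

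**What the plan says.** Section 11.5.7 bases toxicity on the Appendix II schedule: "Each patient will be assessed for the development of toxicity according to the Time and Events table (Appendix II". In Appendix II the row "Adverse event evaluation" is marked weekly during radiation, then at 1, 3, 6, 9 and 12 months after therapy. The Section 10.0 table agrees: "After each weekly treatment visit, then post XRT follow-up at 1, 3, 6, 9, and 12 months". Neither table has a visit between the end of radiation and the 1-month visit.

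Section 6.9 says of routine reporting: "Adverse events are reported in a routine manner at scheduled times during a trial". Its definitions run the acute period from consent to 30 days after treatment, and the late period from there to 2 years after treatment.

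The length of treatment depends on the arm. Arm A (6.1.2): "Patients will receive 4.0 Gy per fraction for 15 fractions (total dose = 60 Gy". Arm B (6.2.2): "Patients on Arm B will receive 30-33 fractions of radiation at 2 Gy per fraction (total dose 60-66 Gy". Both are given daily.

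Section 11.5.7 then tests two things between arms with a two-sided chi-square at 0.05: the rate of Grade 3-5 events, and death during treatment or within 30 days of stopping it. It names no window common to both arms and makes no adjustment for visit frequency or length of observation.

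**The concern.** Three clocks (visit frequency, the acute period and the early-death window) stop or change at an event whose timing is fixed by the randomized arm. Arm B is watched weekly for about twice as long, and its acute and early-death windows are about three weeks longer. With identical true hazards, a longer window collects more deaths and more acute events. More frequent visits may also record more short events. Both effects favor Arm A.

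Toxicity is a secondary endpoint, but it matters here. Section 9.9 raises the possibility that hypofractionation increases normal tissue toxicity and names esophagitis and pneumonitis as the main toxicities. Section 6.9.2 expects a good share of patients to have Grade 3 esophagitis, typically appearing within two weeks of starting treatment, and adds: "Acute esophagitis may persist for 4-6 weeks". In Arm A, much of that course can fall after the last weekly visit.

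**Working it through.** **Step 1. Treatment length.** Five fractions a week is inferred from daily treatment and from the pace of the cohorts cited in Section 1.2: one was "treated to 45 Gy over 3 weeks at 3 Gy/fraction" (15 fractions), the other had 60-66 Gy at 2 Gy over 6 to 6.5 weeks. Weeks = fractions / 5: Arm A 15/5 = 3.0; Arm B 30/5 = 6.0 to 33/5 = 6.6.

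**Step 2. Scheduled visits, in weeks from the start of radiation.** The 1-month visit is at end of radiation + 4.35 weeks.

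| | Weekly visits | 1-month visit | Visits through 1 month |
|---|---|---|---|
| Arm A | 1, 2, 3 | 7.3 | 4 |
| Arm B, 30 fractions | 1 to 6 | 10.3 | 7 |
| Arm B, 33 fractions | 1 to 6, and 6.6 | 10.9 | 8 |

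Between Arm A's last weekly visit and its 1-month visit, Arm A has 0 scheduled visits and Arm B has 3 or 4. All of Arm B's fall by week 6 to 6.6; Arm B then has its own gap of about 4.35 weeks.

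**Step 3. Effect of window length on early death.** The plan's control hazard reproduces: -ln(0.45) = 0.7985, stated as 0.799 per year. Apply it to both arms, so there is no treatment effect, and count deaths of any cause. With a Monday start as day 0, the last fraction falls on day 18 (Arm A), 39 (30 fractions) or 44 (33 fractions). The window ends 30 days later. P(death) = 1 - exp(-0.799 × days / 365.25):

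- Arm A, 48 days: 1 - exp(-0.1050) = 10.0%, or 11.3 of 113
- Arm B, 69 days: 1 - exp(-0.1509) = 14.0%, or 15.8 of 113
- Arm B, 74 days: 1 - exp(-0.1619) = 14.9%, or 16.9 of 113

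Using whole weeks instead (51, 72 and 76.2 days) gives 10.6%, 14.6% and 15.4%. The difference of 4 to 5 percentage points comes from the definition alone.

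**Step 4. Effect of visit frequency on recorded events (illustration only).** Suppose an event is seen only if present at a visit, and onset is uniform. Visits are on days 4, 11, 18 and 48 (Arm A) and 4, 11, 18, 25, 32, 39 and 69 (Arm B, 30 fractions). Onset range, event duration and the share recalled are all assumptions.

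| Time at Grade 3 | Onset days 14-42: A vs B | Onset day 14 to each arm's 1-month visit: A vs B |
|---|---|---|
| 7 days | 18% vs 89% | 32% vs 58% |
| 14 days | 43% vs 89% | 53% vs 71% |
| 21 days | 68% vs 89% | 73% vs 84% |
| 28 days | 93% vs 93% | 94% vs 96% |
| 35 days | 100% vs 100% | 100% vs 100% |

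The first onset range leaves out nearly all of Arm B's own gap (days 39-69), so it exaggerates the contrast. Recall shrinks it further. With that same range, an assumed true rate of 15% in both arms and 80% of missed events recalled, recorded rates are 12.5% (7 days) to 13.3% (14 days) in Arm A against 14.7% in Arm B. That is about 2 patients per 113.

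**The case against.** A reader might infer that Arm A goes unobserved while Arm B is seen weekly up to week 7, and that Grade 3-5 rates will be heavily under-recorded in Arm A. The documents do not support that, for four reasons.

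- Arm B's weekly visits end at week 6 to 6.6, and a similar one-month gap follows. Timed from the end of radiation, the two schedules are the same.
- Section 6.9 defines adverse events by the period in which they occur and follows them to resolution or stability. An Arm A event in week 5 is therefore reportable at the 1-month visit. The adverse event form is not among the documents, so it may already ask about the interval.
- Serious events go to the monitoring committee within 5 business days of awareness in both arms (6.11), which covers inpatient stays of 24 hours or more. The diary (9.8) and the cost worksheet (Appendix VI) also ask about admissions, emergency visits and clinic visits.
- Esophagitis said to last 4 to 6 weeks would usually still be present at the 1-month visit. No document supports 7 to 14 days at Grade 3.

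These points stand, and they limit the recording concern to short, non-serious Grade 3 events that are not recalled. They do not remove it entirely, because Grade 3 esophagitis as defined in 6.9.2 need not involve admission. Nor do they touch window length: deaths are recorded whatever the visit schedule, and Arm B is still given about three more weeks in which to have them.

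A further objection is that a window from enrollment gives Arm A more time after radiation, when pneumonitis appears (6.9.3: weeks to months). That is a real cost. Reporting later events separately and keeping the end-of-treatment window as a supporting analysis meets it.

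**Conclusion.** The concern holds for window length and, more weakly, for recording.

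- **Firm:** the schedules and windows are tied to the end of radiation, giving 4 visits over about 7 weeks in Arm A and 7 or 8 over about 10 to 11 in Arm B. This rests only on five fractions a week.
- **Sized under a stated assumption:** early death of about 10% against 14% to 15% with no treatment effect, using the plan's own control hazard held constant from the first fraction and counting all deaths. Section 11.5.7 limits adverse events to treatment-related ones but does not say whether that covers the death comparison. If it does, the gap would be smaller.
- **Direction only:** short, non-serious Grade 3 events are somewhat less likely to be recorded in Arm A. The size cannot be determined from the documents, and the effect disappears for events of about 4 weeks or with good recall. The capture percentages are illustrations and should not be cited as an estimate of bias.

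The Grade 3-5 comparison names no window at all. If it pools events to 2 years after treatment, the three extra weeks matter little there; they matter for any acute analysis and for early death. Because both effects favor the experimental arm on its main safety question, the comparison rule should be changed.

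**What to change.** **Section 11.5.7.** Compare acute Grade 3-5 events and early deaths over one window of equal length from enrollment in both arms, long enough to cover Arm B's 1-month visit. Radiation may start up to 4 weeks after enrollment (6.1, 6.2), so the longest case is 4 + 6.6 + 4.35 = 14.95, about 15 weeks. Report later events separately. Keep the comparison to 30 days after treatment as a supporting analysis, and state whether it counts all deaths or only treatment-related ones.

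**Section 10.0 and Appendix II.** State that each adverse event assessment records the worst grade since the previous visit, with onset and resolution dates, checked against the cost worksheet already collected at that visit.

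**Cost.** A few sentences and form wording, with no added visits. The downsides are a few more dates to record and a main window that includes about 3 to 3.6 more weeks after radiation for Arm A than for Arm B. The form change still relies on recall between visits, so it reduces the recording difference without removing it.
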